9.8.4. Efficacy-Related Biomarkers

Samples for biomarker assessments will be collected according to the Schedules of Assessments (Table 7 and Table 8). Blood, tissue, and stool samples will be analyzed by the central or specialty laboratory. Details for collection, processing, and storage will be provided in the Laboratory Manual. Residual samples will be stored and may be used for additional analyses if the subject has granted consent where allowed by the regulatory authorities and local ethics committees.

C-reactive protein (CRP): CRP is an acute phase protein expressed by hepatocytes in response to inflammatory cytokines and will be assessed using a hs-CRP assay. Investigators will be blinded to the hs-CRP results during the treatment and follow-up periods.

Fecal calprotectin: Fecal calprotectin is a complex consisting of calcium-binding proteins. It is expressed by activated neutrophils (and to a lesser extent by macrophages and monocytes) and fecal levels correlate with the number of neutrophils in the gut. It is used as a biomarker of intestinal inflammation. Investigators will be blinded to the fecal calprotectin results during the treatment and follow-up periods.

Lymphocyte counts: Etrasimod is believed to modulate lymphocyte trafficking resulting in a reduction in peripheral lymphocyte count and lymphocyte availability for recruitment to sites of inflammation. During the treatment period, the Investigator will be blinded to the white blood cell (WBC) and differential counts during the treatment and follow-up periods. During the

treatment period, WBC differential results will be assessed by an unblinded Medical Monitor (not providing direct medical oversight of study conduct). If either of the following occur, the unblinded Medical Monitor will notify the Investigator with additional instructions.

- ANC < 1000 cells/ μ L
- ALC < 200 cells/ μ L

If the ANC is confirmed below the 1000 cells/ μ L limit, the Investigator will be requested to closely monitor for serious infection and institute appropriate follow-up at his or her discretion.

If the ALC is confirmed below the 200 cells/ μ L limit, study treatment should be interrupted and should not be reinitiated if the ALC remains below this threshold. In this situation, the unblinded Medical Monitor will notify the Investigator and provide instructions on additional actions that the Investigator may need to take. When there is at least one measurement of ALC < 200 cells/ μ L, blinded values may be released to treating physicians and Investigators as deemed medically necessary to monitor infection and/or aid in diagnostic work-up as clinically indicated, and/or as a tool to assess the effectiveness of therapeutic interventions for an infection. Investigators will repeat CBC with differentials weekly until ALC > 500 cells/ μ L.

Re-initiation of the study treatment can only be considered when ALC > 500 cells/ μ L.

[REDACTED]

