5. REMOVAL OF SUBJECTS FROM STUDY TREATMENT OR ASSESSMENT

5.1. Discontinuation from Study Treatment

A subject's double-blind treatment may be discontinued for any of the following reasons:

- Worsening of disease (Note: If a subject discontinues double-blind treatment at any time starting with the Week 12 assessment, the subject may be eligible to enter the APD334-303 OLE [Section 5.1.1])
- Adverse event that in the judgement of the Investigator and/or Medical Monitor the subject should not continue study treatment
- Subject noncompliance with the protocol or study treatment that is considered significant by the Medical Monitor
- Investigator decision
- Withdrawal by subject or parent/guardian
- Lack of efficacy
- Lost to follow-up
- Study termination by Sponsor
- Other, non-adverse event

A subject's double-blind treatment must be discontinued for any of the following reasons:

- Decline in PFT values (FEV₁ and/or FVC) below 50% of the predicted values
- Confirmed diagnosis of clinically significant macular edema
- Confirmed diagnosis of active TB
- Subjects who have a cardiovascular treatment-related symptomatic event (eg, chest pain, dizziness, palpitations, lightheadedness, shortness of breath, or syncope) associated with reduction of the heart rate or associated with clinically relevant ECG changes at any time during the 4-hour monitoring period on Day 1 or Day 2 (as applicable) (Section 9.4.2.1)
- Subjects who have not met the discharge criteria on Day 1 after ≥ 4 hours of extended monitoring, or Day 2 by 4 hours post-dose (Table 4).
- Pregnancy (Section 9.10.9)
- Suspected drug induced liver injury as defined by the 2009 FDA Guidance for Industry (FDA 2009)
 - ALT or AST $> 8 \times$ ULN
 - ALT or AST $> 5 \times$ ULN for > 2 weeks
 - ALT or AST $> 3 \times$ ULN and (total bilirubin $> 2 \times$ ULN or international normalized ratio > 1.5)
 - ALT or AST $> 3 \times$ ULN with the appearance of fatigue, nausea, vomiting, right upper quadrant pain or tenderness, fever, rash, and/or eosinophilia ($> 5\%$)

Because transient fluctuations of ALT or AST are common, and progression to severe drug-induced liver injury or acute liver failure is uncommon, automatic discontinuation of study treatment upon finding a greater than $3 \times$ ULN elevation of ALT or AST may be unnecessary.

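### No written step makes sure the mandatory liver stopping rule in Protocol 5.1 is applied when eosinophilia is the only accompanying sign, because 9.8.4 blinds the differential and sets only ANC and ALC triggers

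*Protocol*

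**What the plan says.** - **The stopping rule (Protocol 5.1).** Suspected drug-induced liver injury stands in the list headed by the statement that "double-blind treatment must be discontinued for any of the following reasons". It has four criteria. The fourth is ALT or AST > 3 × ULN with fatigue, nausea, vomiting, "right upper quadrant pain or tenderness, fever, rash, and/or eosinophilia" (> 5%).
- **The softening sentence (Protocol 5.1).** After the criteria, the protocol adds that "automatic discontinuation of study treatment upon finding a greater than" 3 × ULN rise in ALT or AST may not be needed.
- **The blinding (Protocol 9.8.4).** Under the entry on lymphocyte counts, "the Investigator will be blinded to the white blood cell (WBC) and differential counts during the treatment and follow-up periods".
- **Who reads the differential (Protocol 9.8.4).** The reader is a monitor outside the day-to-day medical oversight of the study. The notification sentence, "If either of the following occur, the unblinded Medical Monitor will notify the Investigator with additional instructions", is followed by two events: ANC < 1000 and ALC < 200 cells/µL.
- **Release of blinded values (Protocol 9.8.4).** The condition comes first: "When there is at least one measurement of ALC" < 200 cells/µL. Then "blinded values may be released to treating physicians and Investigators as deemed medically necessary to monitor infection and/or aid in diagnostic work-up as clinically indicated".
- **Table 6, footnote a.** The footnote is attached to the white-cell-count-with-differential row. It keeps Investigators blinded after randomization and ties the monitor's instructions to significant lymphopenia. It does not name eosinophils.

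**The concern.** A stopping rule works only if someone who can act on it learns that it has been met. The site sees ALT and AST. On the wording of 9.8.4, it does not see the eosinophil result. The person who does see it is required to speak up for two other reasons only.

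Take a subject with ALT or AST above 3 × ULN, eosinophils above 5%, no other listed sign and no other liver criterion met. That subject must be stopped under 5.1. A site that follows the visible text could keep dosing without knowing this, and the softening sentence would make that look consistent with the protocol. What is at stake is one mandatory safety rule in a rare configuration. No efficacy endpoint, estimand or error rate is involved.

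**Working it through.** No figure in the plan needs reproducing. The check sets the sections side by side and follows the eosinophil result from sample to site.

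1. **Is eosinophilia alone enough?** Yes. The fourth criterion joins its signs with and/or, so any one of them with ALT or AST > 3 × ULN is sufficient. There are 7 signs: fatigue, nausea, vomiting, right upper quadrant pain or tenderness, fever, rash and eosinophilia. The site can observe 7 − 1 = 6 of them directly.

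2. **Which laboratory inputs do the four criteria need?** Five: ALT, AST, total bilirubin, INR and eosinophils. No blinding text touches the first four. Only eosinophils fall under a blinding statement, on the wording of 9.8.4.

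3. **Does a required notification cover it?** No. The ANC and ALC triggers do not depend on eosinophils or on ALT or AST. Outside 5.1, no visible text in the protocol or SAP mentions eosinophils.

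4. **Does another written route carry the result to the site?**
   - Release of blinded values under 9.8.4 opens only after an ALC < 200 cells/µL.
   - Protocol 9.1 sends urgent safety concerns to the Medical Monitor. No step links that contact to the unblinded monitor who reads the differential.
   - Protocol 9.10.7 has clinically significant abnormal tests repeated and sets a recording rule for local results. It does not ask for a differential when ALT or AST is high.
   - Emergency unblinding under 6.5 gives the treatment assignment, not a laboratory value.

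5. **How narrow is the case?** All of these must hold together: ALT or AST > 3 and not > 8 × ULN; not > 5 × ULN for > 2 weeks; total bilirubin not > 2 × ULN; INR not > 1.5; none of the six visible signs; eosinophils > 5%. The documents give no rate for this combination, so no number of subjects is claimed.

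6. **Do the data to apply the rule exist?** Yes. Tables 7 and 8 schedule the CBC with differential and the chemistry panel together at 4 visits (Weeks 2, 4, 8, 12) and 7 visits (Weeks 16, 20, 24, 32, 40, 48, 52): 4 + 7 = 11 post-baseline treatment visits. An unblinded reader is already in place.

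**The case against.** A reader might infer that 5.1 and 9.8.4 contradict each other and that the eosinophilia rule cannot operate. The documents do not support that.

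- The monitor assesses the whole differential. The ANC and ALC events are those on which notice must be given, and nothing says they are the only ones on which it may be.
- Section 5.1 does not reserve its stopping criteria to the Investigator. Its adverse-event ground, in the list of permitted reasons, names the Medical Monitor as well.
- A local differential is not forbidden. Section 9.10.7 expects local results that change a subject's management. Section 9.5 sends some subjects for a local CBC with differential in follow-up, when 9.8.4 still blinds the Investigator. A local differential would show the lymphocyte count, which is a cost to blinding but not a bar.

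The premise that eosinophils are blinded can also be questioned. Section 9.10.7 takes only total WBC and ALC out of the Investigator's review of the laboratory report. Table 6 footnote a names total WBC, neutrophils, lymphocytes and CD4 T cells as the counts the monitor reviews after randomization. Against this, 9.8.4 says differential counts without exception, 9.10.7 defers to 9.8.4, and the footnote is attached to the whole differential row. The better reading is that eosinophils are blinded, but it is not beyond dispute. If they were meant to be visible, the three places disagree and still need one clarifying line.

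A step could also sit in the redacted block at the end of 9.8.4 or in the Laboratory Manual. Neither can be checked.

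Finally, the subject is not unmanaged. The site sees the enzymes, bilirubin and INR, and may stop on its own judgement. All of these points stand. They reduce the size of the concern but do not supply the missing step.

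**Conclusion.** The concern holds as a missing link in the visible text. Eosinophilia above 5% with ALT or AST above 3 × ULN is a mandatory reason to stop, and no written step makes sure anyone applies it when eosinophilia is the only accompanying sign. The softening sentence in 5.1 concerns the enzyme rise and does not cancel the combined criterion.

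The severity is minor: one sign of seven in one criterion of four, with Investigator judgement still available. Confidence is moderate. The conclusion rests on two assumptions: that 9.8.4 governs over the less clear wording of 9.10.7 and Table 6 footnote a, and that the unseen text contains no such step. If the sponsor can point to one, the concern is answered.

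**What to change.** Add a third notification trigger to Protocol 9.8.4 and repeat it in Table 6 footnote a:

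*ALT or AST > 3 × ULN with same-sample eosinophils > 5%: the unblinded Medical Monitor informs the Investigator that the 5.1 criterion is met, without releasing WBC, lymphocyte or eosinophil values.*

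Values should be withheld because an absolute eosinophil count with its percentage gives back the blinded WBC: WBC = absolute eosinophils / eosinophil fraction. With assumed values of 0.20 × 10⁹/L and 6%, WBC = 0.20 / 0.06 = 3.33 × 10⁹/L.

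Costs:
- A central-laboratory alert to the unblinded monitor when ALT or AST exceeds 3 × ULN.
- Inclusion in a protocol amendment, with the IRB/IEC approval that Protocol 11.2 requires. No new sample or visit is needed.
- A small hint of treatment. Etrasimod lowers lymphocytes (Protocol 1.3), which shrinks the denominator of the eosinophil percentage. For an absolute eosinophil count E, the 5% line is crossed once WBC falls below E / 0.05 = 20E; with the same assumed E of 0.20 × 10⁹/L, that is 0.20 / 0.05 = 4.0 × 10⁹/L. Some notices on active drug could therefore reflect fewer lymphocytes rather than more eosinophils. The hint is confined to subjects already above 3 × ULN.

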9.9. Genetics

Genetics will be evaluated in this study to assess genetic variation that may impact response to treatment, metabolism, and mechanism of action of etrasimod. DNA may be used for immunophenotyping by epigenetic profiling.

A blood sample for DNA isolation will be collected from subjects who have consented to participate in the genetic analysis component of the study. Participation is optional. Subjects who do not wish to participate in the genetic research may still participate in the study.

In the event of DNA extraction failure, a replacement genetic blood sample may be requested from the subject.

Details on the processes for collection and shipment and destruction of these samples can be found in the Laboratory Manual.

9.10. Safety

The Investigator or site staff will be responsible for detecting, documenting, and reporting events that meet the definition of an adverse event or SAE (Section 9.10.8.1). Adverse events will be coded using the latest version of the Medical Dictionary for Regulatory Activities (MedDRA).

9.10.1. Physical Examination

Full and symptom-directed physical examinations will be performed according to the Schedules of Assessments (Table 7 and Table 8).

Full physical examination includes the following assessments:

- General inspection
- Weight/height (height at screening only)
- Skin
- Head/ears/eyes/nose/throat examination
- Neck
- Cardiac examination
- Auscultation of lungs
- Abdominal examination (liver, spleen, and lower abdomen)
- Neurological assessment
- Musculoskeletal assessment to include lower extremity edema evaluation

Symptom-directed (focused) physical examinations should assess clinically significant changes from full physical examinations or any new signs or symptoms.

9.10.2. Vital Signs

Resting vital signs measurements will be performed according to the Schedules of Assessments (Table 7 and Table 8) with the subject in the sitting position. Vital signs will be measured prior to any blood draws that occur at the same study visit.

Blood pressure may be measured manually or by automated device. Proper technique should be utilized during the measurement of BP to include the following:

- The subject's arm should be bare and supported at heart level.
- An appropriately sized cuff (cuff bladder encircling at least 80% of the arm) should be utilized. Subject's legs should not be crossed during the evaluation.

9.10.3. 12-Lead Electrocardiogram

All 12-lead ECGs will be performed according to Section 9.4.2.1 and the Schedules of Assessments (Table 7 and Table 8), and if clinically indicated at any time during the treatment period per Investigator discretion. All ECGs will be recorded from a 12-lead ECG machine with the subject in the supine position. Every attempt should be made to ensure the subject 12-lead ECG readings are obtained using the same machine throughout the study.

Intervals to be provided on the confirmed read for each safety 12-lead ECG are: RR, PR, QRS, QT, and QTcF. If an ECG shows a new onset QTc interval > 500 ms during the treatment period, a repeated ECG is warranted. If this abnormal finding is confirmed, study treatment must be interrupted. Effective diagnostic and therapeutic strategies should be employed.

Reversible causes of prolonged QTc interval (eg, electrolyte abnormalities or hypomagnesemia), should be corrected as clinically indicated. When evaluating a subject with new onset QTc interval above 500 ms, referral to a cardiologist experienced in treating cardiac conduction disorders should be considered. Re-initiation of study treatment can only be considered after all of the following have occurred:

- The QTcF interval is < 450 ms (men) or < 470 ms (women)
- The QTc prolongation is considered by the Investigator and confirmed by the cardiologist as not related to study treatment and likely caused by other factors
- Individual risk-benefit is favorable (as determined by the Investigator, in agreement with the cardiologist), **AND**
- After discussion with the Medical Monitor.

The Investigator will be responsible for review and interpretation of 12-lead ECGs on site and determining if the 12-lead ECG is normal, abnormal clinically insignificant, or abnormal clinically significant. Findings will be documented in the eCRF.

All 12-lead ECGs performed should be available for collection upon request.

9.10.4. Pulmonary Function Test

Pulmonary function tests will be performed according to the Schedules of Assessments (Table 7 and Table 8) and includes FEV₁ and FVC measurements. All subjects will have PFTs performed at Screening, Week 12, and Week 52, or at the ET visit. PFTs occurring at the ET visit that are

within 4 weeks of the last assessment (eg, Week 12) will only be required if clinically indicated. The 2-Week Follow-Up visit assessment is only required if clinically indicated.

Subjects with a history of mild pulmonary disease (eg, asthma, chronic obstructive pulmonary disease) will have additional PFTs performed at Week 32. Subjects reporting respiratory adverse events such as dyspnea during the treatment period may return at an unscheduled visit for assessment per Investigator discretion; additional PFTs may be performed as clinically indicated.

Subjects experiencing a decline in PFT values (FEV₁ and/or FVC) below 50% of the predicted values must be discontinued from study treatment and scheduled for a follow-up visit.

When available, DLCO measurements will also be performed. When DLCO is not available, sites should consult the Sponsor or Sponsor's delegate. These tests will be performed at a qualified pulmonary function laboratory or respiratory department. Please refer to the American Thoracic Society/European Respiratory Society guidelines for standardization of spirometry and single breath determination of carbon monoxide uptake in the lung ([MacIntyre 2005](#), [Miller 2005a](#), [Miller 2005b](#)).

The safety of trial subjects and site staff is paramount, so it is at the Investigator's discretion whether PFT can be safely administered to trial subjects during the treatment period. The Investigator should evaluate on a case-by-case basis how best to proceed based on the subject's medical history, the Investigator's clinical judgment, and in consultation with the Medical Monitor. All reasonable efforts should be made to ensure safety and adherence to the protocol. When available, spirometry may be conducted at the clinical site instead of at the pulmonary laboratory. If the decision is made that it is not appropriate to conduct PFTs due to the safety concerns (eg, COVID-19 transmission), then this decision and rationale should be appropriately captured in the subject's source documentation. When available and safe (due to lifting of local restrictions, re-opening of local PFT labs, or improved safety conditions) the tests should be conducted as soon as possible and as close to the timepoints as outlined in the protocol.

9.10.5. Ophthalmoscopy and Optical Coherence Tomography

A complete ophthalmoscopy and OCT assessment will be performed according to the Schedules of Assessments ([Table 7](#) and [Table 8](#)). OCTs occurring at the ET visit that are within 4 weeks of the last assessment (eg, Week 12) will only be required if clinically indicated. The 2-Week Follow-Up visit assessment is only required if clinically indicated. A standard visual acuity chart should be used for the visual acuity assessment. The OCT machine used should preferably not be changed during the study to allow for comparison of central foveal thickness measurements within each subject across timepoints.

Screening visit:

At the screening ophthalmology visit, the eye examination will include:

- Ophthalmologic history
- Best corrected visual acuity measurement (using Snellen chart internationally [if available])
- Ophthalmoscopy (may include contact lens biomicroscopy to examine the macula and optic disc). A dilated fundus exam should be performed in all subjects at the

screening visit and as needed at subsequent visits in subjects with significant abnormalities identified on the screening exam.

- Measurement of central foveal thickness by OCT (recorded in micrometers; required for all subjects regardless of the results of visual acuity or ophthalmoscopy) Slit lamp examination should be performed to establish uveitis disease status (yes/no). Uveitis should be characterized and graded using the Standardization of Uveitis Nomenclature criteria. Subjects with active uveitis without macular edema at Screening are eligible to enroll in the study
- If there is a suspicion of macular edema by ophthalmoscopy and increased central foveal thickness by OCT, then additional testing should be considered at the discretion of the ophthalmologist (for example, fluorescein angiogram may be performed). Subjects with diagnosed macular edema at Screening should be deemed a screening failure and should not be randomized.
- Optional procedures in case of clinically significant abnormalities on ophthalmic exam may include but are not limited to:
 - Retinal photographs
 - Intraocular pressure

Scheduled post-screening visits:

At the scheduled ophthalmology visit, the eye examination will include

- Best corrected visual acuity measurement
- Ophthalmoscopy (may include contact lens biomicroscopy to examine the macula and optic disc)
- Measurement of central foveal thickness by OCT
- For subjects with uveitis findings on ophthalmic exam, additional testing should be considered (for example, fluorescein angiogram).

Subjects experiencing unexpected ophthalmic symptoms without a known suspected etiology or experiencing a relevant ophthalmic AE may need to have repeated ophthalmoscopy and OCT testing performed.

9.10.6. Tuberculosis Screening and Chest X-Ray

All subjects will complete TB screening to determine eligibility. A TB screening questionnaire will be completed during the Screening Period by the PI or delegated site staff for each subject and applicable information will be entered into the eCRF. For subjects residing in countries with a high burden of TB or multi-drug resistant (MDR) TB as identified by WHO, the TB screening questionnaire will be completed at every study visit ([Appendix 2](#)). For subjects who are receiving TB prophylaxis treatment, the TB questionnaire will be completed at every study visit (until TB prophylaxis treatment course is completed).

